## 2) Background

The incidence of hepatocellular carcinoma (HCC) has recently increased in the US mostly due to an increase in chronic hepatitis C infection. Angiogenesis is critical for the growth and metastatic progression of HCC, and involves different molecular pathways including VEGF (vascular endothelial growth factor) which is released following a hypoxic stimulus, inducing hyperpermeability of tumor vessels. The arterial vascular profile of HCC has provided the basis for the use of transarterial chemoembolization (TACE) as an effective therapy to cause tumor necrosis. Imaging plays an essential role in HCC screening, diagnosis and staging. However, the assessment of HCC tumor grade and aggressiveness, and the prediction of response of HCC to TACE using imaging criteria are not established. With the development of new antiangiogenic drugs recently approved in advanced human HCC, such as sorafenib, imaging methods to predict and assess therapeutic response beyond changes in size become critical. It has been recently suggested that assessing the degree of residual tumor enhancement on dynamic CT or MRI using modified RECIST (mRECIST) criteria in HCC treated with TACE or systemic therapy is more appropriate than the use of conventional RECIST criteria (which are based on size only).

Recently, functional MRI methods have shown promising results for evaluation of tumor cellularity and grade, angiogenesis and hypoxia. Apparent diffusion coefficient (ADC) measured with diffusion-weighted imaging (DWI) has been correlated with tumor cellularity in brain, prostate and breast tumors and with HCC tumor grade, and has been used for assessment of response of HCC to TACE. BOLD (blood oxygen level dependent) MRI experiments have demonstrated a decrease in  $R2^*$  after oxygen or

	Protocol Name:	Evaluation of HCC Response to Systemic Therapy with Quantitative MRI
	Principal Investigator:	[name]
	Primary Contact Name/Contact Info:	[name] [contact] [contact]
	Date Revised:	6/30/2017
	Study Number:	GCO12-0214

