ADC measured with DWI has been shown to correlate negatively with tumor cellularity in brain, breast and prostate tumors. Recent data suggest a correlation between tumor ADC and HCC grade. ADC is also increasingly applied to evaluate tumor response to local or systemic therapy in liver tumors. Pre-clinical and clinical studies have shown that effective tumor treatment results in a rise in tumor ADC, which can occur prior to any measurable change in tumor size. Following the increase in ADC with treatment, the ADC will subsequently fall, related to tumor repopulation, fibrosis or tissue remodeling and decreased perfusion. There are several reports on the use of ADC to evaluate HCC response to chemo- or radioembolization. These studies demonstrated measurable differences before and after treatment. There is very limited published data on the use of DWI after treatment of HCC with sorafenib, and no data on the use of DWI for predicting response of HCC to therapy.

BOLD MRI can detect oxygenation changes secondary to changes in blood flow and deoxyhemoglobin in tumors. Deoxyhemoglobin acts as an endogenous paramagnetic MRI contrast agent by reducing apparent transverse relaxation time ( $R2^*$ , in  $\text{sec}^{-1}$ ) of neighboring tissues. BOLD MRI technique detects these relative changes in  $R2^*$ . In various murine cancer models, significant changes in tumor  $R2^*$  were demonstrated when altering concentrations of  $O_2$  administration. Rhee et al demonstrated an increase in  $R2^*$  values after HCC embolization in rabbits.

DCE-MRI has been used to study tumor pathophysiology and to follow antiangiogenic treatments. With the proposed concept of perfusion “normalization” with antiangiogenic therapy, a decrease in perfusion and blood volume is expected in tumors, however data on DCE-MRI in HCC treated with systemic

	Protocol Name:	Evaluation of HCC Response to Systemic Therapy with Quantitative MRI
	Principal Investigator:	[name]
	Primary Contact Name/Contact Info:	[name] [contact] [contact]
	Date Revised:	6/30/2017
	Study Number:	GCO12-0214

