**Exclusion criteria**

1. Age less than 18 years.
2. Unable or unwilling to give informed consent.
3. Contra-indications to MRI and/or PET/MRI
  - a. Electrical implants such as cardiac pacemakers or perfusion pumps
  - b. Ferromagnetic implants such as aneurysm clips, surgical clips, prostheses, artificial hearts, valves with steel parts, metal fragments, shrapnel, tattoos near the eye, or steel implants
  - c. Ferromagnetic objects such as jewelry or metal clips in clothing
  - d. Pregnant subjects
  - e. Pre-existing medical conditions including a likelihood of developing seizures or claustrophobic reactions.

Patients with GFR <30 will not undergo DCE-MRI with Gadolinium contrast. For patients with GFR < 30, we will still consider enrolling patients for a non-contrast MR protocol, including non-contrast sequences (DWI, BOLD and MRE). Patients with severe COPD will not undergo oxygen-enhanced sequences, due to risk of respiratory decompensation. Patients with uncontrolled diabetes will not undergo the PET/MRI study. Uncontrolled Diabetes” will be defined by high blood levels of glucose observed over 200 mg/dl secondary to untreated diabetes or to incompletely treated diabetes.

As with all patients referred for MRI and PET/MRI, each patient is screened for possible contraindications with a routine questionnaire.

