**d) Study Timelines**

Duration of the study is 3 Years.

All subjects will undergo 1 to 2 MRI exams and ARFI.

We would like to ask a subset of 23 additional patients out of 150 if they are willing to undergo a PET/MRI study and ARFI.

We propose to assess response of therapy in a subset of 30 patients with unresectable HCC. These patients will be selected when they undergo treatment with systemic therapy such as sorafenib

	Protocol Name:	Evaluation of HCC Response to Systemic Therapy with Quantitative MRI
	Principal Investigator:	[name]
	Primary Contact Name/Contact Info:	[name] [contact] [contact]
	Date Revised:	6/30/2017
	Study Number:	GCO12-0214

(indicated clinically) or immunotherapy (using nivolumab) and/or radioembolization (indicated clinically). These patients will be imaged before treatment and 2-4 weeks after initiating therapy. Imaging will involve MRI only.

The total examination time per visit including the setup and routine MRI/ARFI/PET/MRI will be approximately 60-90 minutes.

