#### e) Endpoints

- *Tumor response*: defined as the % of tumor necrosis diagnosed on image subtraction on subsequent routine clinically indicated MRI performed 3-6 months after initiating therapy.
- *Time to tumor progression*: defined as the time from initiating therapy to disease progression according to mRECIST criteria as diagnosed on follow-up routine contrast-enhanced MRI. Progression will be defined as an increase of at least 20% in the sum of the diameters of viable target lesions, taking as reference the smallest sum of the diameters of viable target lesions recorded since initiation of therapy.
- *Overall survival*: defined as the time from initiating therapy to death.

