#### f) Procedures Involved in the Human Research

All subjects will undergo 1 to 2 MRI exams and ARFI. During each visit, we will obtain the following MR parameters (DWI, BOLD, MRE and DCE-MRI). Patients referred for MR evaluation of the abdomen will receive all conventional MRI necessary to address the referral indication in addition to DWI, DCE-MRI, BOLD and MRE.

23 patients will be asked to undergo a single PET/MRI and ARFI study. These patients will not be asked to come back for a second PET/MRI study.

We will perform an independent prospective study in up to 30 additional patients with advanced HCC treated with sorafenib or nivolumab and/or Y90 to assess the role of pre-treatment and early changes in quantitative MR parameters for predicting tumor response, time to tumor progression and overall survival.

**Diffusion-weighted MRI (DWI)** will be performed using multiple single shot Echo Planar Imaging (EPI) or segmented EPI acquisitions or non EPI sequences with selected varied parameters and gradients. Diffusion parameters will be calculated (ADC: apparent diffusion coefficient, D: true diffusion coefficient, PF: perfusion fraction).

**BOLD MRI**: Before contrast injection, we will use a breath-hold multiecho T2\* sequence covering the whole liver under room air and after 20 min. of administration of pure O2 (10 L/min) and/or carbogen (95% oxygen and 5% carbon dioxide) through a facial mask or a cannula.

**MR Elastography**: Will be performed before contrast injection. The subject/patient will be asked to perform multiple breath-holds during the image acquisition.

**DCE-MRI** will be performed prior and after intravenous administration of Gadolinium chelates using a 2D or 3D fast T1-weighted sequence. An FDA approved gadolinium contrast agent will be administered. These include extra-cellular agents such as Gd-BOPTA (Multihance), a liver specific

	Protocol Name:	Evaluation of HCC Response to Systemic Therapy with Quantitative MRI
	Principal Investigator:	[name]
	Primary Contact Name/Contact Info:	[name] [contact] [contact]
	Date Revised:	6/30/2017
	Study Number:	GCO12-0214

agent such as Gd-EOB-DTPA (Eovist), and a blood-pool agent (gadofovesettrisodium, Ablavar). As the contrast is circulating through the body the patient will be imaged for approximately 5 minutes after contrast injection. The patient will hold his/her breath for as long as possible.

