#### *Very rare, but serious*

- Nephrogenic systemic fibrosis (NSF)/Nephrogenic Fibrosing Dermopathy (NFD). NSF is a condition associated with the gadolinium contrast agent when there is severe kidney disease. Symptoms include tightening or scarring of the skin and organ failure. In some cases, it can be deadly. NSF has not been seen in patients with normal working kidneys or mild problems in kidney function.

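### Are the therapy-cohort endpoints unusable because response and progression come only from routine follow-up MRI and no rule covers early deaths?

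*Combined protocol and SAP*

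**What the plan says.** Section 5(e) lists three outcomes for patients treated with systemic therapy or radioembolization.

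- Tumor response is "defined as the % of tumor necrosis diagnosed on image subtraction on subsequent routine clinically indicated MRI performed 3-6 months after initiating therapy".
- Time to progression runs to "disease progression according to mRECIST criteria as diagnosed on follow-up routine contrast-enhanced MRI", with a threshold of a 20% increase in viable target diameters over the smallest sum recorded.
- Overall survival runs from start of therapy to death.

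Section 5(f) gives the cohort's purpose as "predicting tumor response, time to tumor progression and overall survival", in up to 30 patients. Section 5(d) sets the study scans: "These patients will be imaged before treatment and 2-4 weeks after initiating therapy. Imaging will involve MRI only".

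Under the exclusion criteria in 5(b), gadolinium DCE-MRI is withheld when GFR is below 30, and the text adds: "For patients with GFR < 30, we will still consider enrolling patients for a non-contrast MR protocol". The HRP-213 modification form of 5/11/18 adds iRECIST to mRECIST for dating progression. The text supplied contains no rule for a missing response value or for death before progression.

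**The concern.** Two of the three outcomes depend on a later scan that the study does not schedule. In advanced HCC some patients will die first, and those deaths are unlikely to be unrelated to response. A correlation between an early marker and necrosis would then describe scanned survivors only.

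Four further points seem to add to this.

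- **Kidney function.** Patients with GFR below 30 can enrol without contrast, yet progression needs a contrast-enhanced scan and subtraction imaging appears to need one. Section 6 says "NSF is a condition associated with the gadolinium contrast agent when there is severe kidney disease", so such patients might have neither outcome.
- **Modality.** The Background describes "assessing the degree of residual tumor enhancement on dynamic CT or MRI using modified RECIST (mRECIST) criteria", while 5(e) names MRI alone. A patient followed by CT would have no progression date.
- **Scan date.** The response window is three months wide, and the Background says of diffusion: "Following the increase in ADC with treatment, the ADC will subsequently fall, related to tumor repopulation, fibrosis or tissue remodeling". Values at 3 and 6 months might not be comparable.
- **Criteria.** From 2018 there are two progression criteria, and the form names neither as the main one.

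At stake would be lost patients, a result of unclear scope, and room to choose evaluability and censoring rules after seeing the data.

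**Working it through.** **Inputs.** From the documents: 30 patients and a response scan at 3-6 months. No alpha, power, effect size, survival, renal or CT figure is stated for this cohort, so there is no planned figure to reproduce. Assumed: exponential survival with median m of 18, 12 or 8 months, scan date uniform over 3-6 months, two-sided alpha 0.05, true marker-response correlation 0.5.

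**Deaths before the scan.** The average of 1 - 0.5^(t/m) over t from 3 to 6 is 1 - [m/(3 ln 2)] × [0.5^(3/m) - 0.5^(6/m)].

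| Median OS (months) | Dead before scan | Of 30 | Left with a value | If a further 20% of survivors lack a contrast MRI |
|---|---|---|---|---|
| 18 | 16% | 5 | 25 | 20 |
| 12 | 23% | 7 | 23 | 18 |
| 8 | 32% | 10 | 20 | 16 |

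For m = 12: 1 - 5.771 × (0.8409 - 0.7071) = 0.228.

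**Loss of precision.** The smallest correlation detectable with 80% power, by the Fisher z approximation, is tanh(2.80/√(n-3)). That is 0.49 at n = 30 and tanh(2.80/√17) = 0.59 at n = 20. Simulated power of a rank correlation is 77% at n = 30. Among scanned patients it is 68 / 65 / 57% for the three medians if death is unrelated to response, and 61 / 53 / 47% if poor response raises the death hazard 2.7-fold per SD.

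**Bias.** The mean observed rank correlation moves only from 0.47 to 0.41-0.46. With no true association, false positives are 4-6% when death depends on response alone. They rise to about 10-13% only when the marker itself also carries a hazard ratio of 2.7 per SD for death (a separate set of runs gave 8-11%).

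**Would ranking deaths as the worst response do better?** Power becomes 44 / 33 / 23% if death is unrelated to response, against 68 / 65 / 57% for scanned-only. At hazard ratio 2.7 it is 64 / 58 / 53%, against 61 / 53 / 47%. Neither method wins throughout.

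**Would adjusting for scan day do better?** If necrosis drifts by 0 / 0.25 / 0.5 / 1 SD per month, power is 77 / 76 / 68 / 51% unadjusted and 76 / 75 / 75 / 73% adjusted. But the date is set by clinical need, so it may itself reflect response. I simulated 30 patients with no drift and a scan date correlated 0 / 0.5 / 0.7 / 0.8 with response (3,000 replicates each, partial rank correlation). Adjusted power was 75 / 64 / 51 / 39%, with unadjusted power unchanged at about 77%.

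**Time to progression.** With a log hazard ratio of 0.5 per SD, power is Φ(0.5√events - 1.96). That gives 78 / 74 / 69 / 63% for 30 / 27 / 24 / 21 events. The 78% assumes that all 30 patients have a recorded progression. If 8-14 die without one (an upper-end assumption: median progression 5 months, independent of death), at most 22-16 events remain and power is 65-52% before any other loss.

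For handling those deaths at log hazard ratio 0.6, censoring gives 52-64% and counting them as events gives 77-79% if the marker predicts both outcomes. If it predicts progression only, the figures are 48-63% and 27-47%. The better choice depends on an unknown.

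**Passages side by side.** The GFR rule in 5(b) limits the study's own DCE-MRI. The endpoints in 5(e) come from routine clinical MRI, which that rule does not govern. The mention of CT in the Background describes mRECIST in general. The rise and fall described there concerns ADC, whereas the endpoint is percent necrosis.

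**The case for a change.** The strongest case for a change is the early-death gap, which needs no inference. The response value exists only for patients alive and scanned at 3-6 months, the study schedules no scan then, and nothing supplied says what happens to the rest. Writing the rule down would cost a few sentences and some data fields, and would close off choices made after seeing outcomes. That much stands as a description of the text, and a careful report would say that the response result applies to scanned survivors.

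The other parts are weaker.

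- **Kidney function.** That a patient with GFR below 30 would also lack a routine contrast scan is plausible but not stated. The plan says only that enrolment will be considered, and no number is given. The two sections leave a case unaddressed; they do not contradict each other.
- **Modality.** One imaging modality is a legitimate choice in a quantitative-MRI study. Accepting CT would gain coverage at the price of between-modality variation in progression dates.
- **Scan date.** Drift in necrosis is an assumption without support in the text, and at 0.25 SD per month the loss is one point of power.
- **Criteria.** The 2018 form summarises a revised protocol that was not supplied. A one-line entry cannot show that the revision names no main criterion. The protocol supplied names one criterion, with a threshold and a reference.

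**Conclusion.** The gap is real but small in consequence, and analysts fill it sensibly. Time to progression is defined by progression, and death has its own endpoint, so censoring deaths without progression at the last evaluable scan is the ordinary reading. Response can be analysed only where it was measured, and reporting how many patients have no value, and why, is normal practice. Overall survival covers every treated patient whatever their imaging.

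The likely cost is a drop from 30 to about 20-25 patients with a response value, or 16-20 if a fifth of survivors also lack a contrast MRI, with little bias unless the marker strongly predicts death. These figures rest on assumed median survival of 8-18 months, a correlation of 0.5 and the assumed hazard ratios. They undercut no stated target: the plan claims no power here, the cohort is up to 30, and the hypothesis in Section 1 says only that MR parameters may enable prediction.

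The substantive alternatives (ranking deaths worst, counting deaths as progression, adjusting for scan day, accepting CT) are trade-offs that improve matters under some assumptions and worsen them under others. The rest would only write down what a competent analysis would do. No change to the plan is called for.

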#### f) Procedures Involved in the Human Research

All subjects will undergo 1 to 2 MRI exams and ARFI. During each visit, we will obtain the following MR parameters (DWI, BOLD, MRE and DCE-MRI). Patients referred for MR evaluation of the abdomen will receive all conventional MRI necessary to address the referral indication in addition to DWI, DCE-MRI, BOLD and MRE.

23 patients will be asked to undergo a single PET/MRI and ARFI study. These patients will not be asked to come back for a second PET/MRI study.

We will perform an independent prospective study in up to 30 additional patients with advanced HCC treated with sorafenib or nivolumab and/or Y90 to assess the role of pre-treatment and early changes in quantitative MR parameters for predicting tumor response, time to tumor progression and overall survival.

**Diffusion-weighted MRI (DWI)** will be performed using multiple single shot Echo Planar Imaging (EPI) or segmented EPI acquisitions or non EPI sequences with selected varied parameters and gradients. Diffusion parameters will be calculated (ADC: apparent diffusion coefficient, D: true diffusion coefficient, PF: perfusion fraction).

**BOLD MRI**: Before contrast injection, we will use a breath-hold multiecho T2\* sequence covering the whole liver under room air and after 20 min. of administration of pure O2 (10 L/min) and/or carbogen (95% oxygen and 5% carbon dioxide) through a facial mask or a cannula.

**MR Elastography**: Will be performed before contrast injection. The subject/patient will be asked to perform multiple breath-holds during the image acquisition.

**DCE-MRI** will be performed prior and after intravenous administration of Gadolinium chelates using a 2D or 3D fast T1-weighted sequence. An FDA approved gadolinium contrast agent will be administered. These include extra-cellular agents such as Gd-BOPTA (Multihance), a liver specific

	Protocol Name:	Evaluation of HCC Response to Systemic Therapy with Quantitative MRI
	Principal Investigator:	[name]
	Primary Contact Name/Contact Info:	[name] [contact] [contact]
	Date Revised:	6/30/2017
	Study Number:	GCO12-0214

agent such as Gd-EOB-DTPA (Eovist), and a blood-pool agent (gadofovesettrisodium, Ablavar). As the contrast is circulating through the body the patient will be imaged for approximately 5 minutes after contrast injection. The patient will hold his/her breath for as long as possible.

**Routine MR sequences** including T1 in and out-of-phase and T2 weighted-imaging will be obtained in all cases.

**FGD-PET/MRI :** The PET/MRI exam should last approximately 60 minutes and will include FDG-PET, DWI, BOLD with room air and then oxygen, DCE-MRI and routine MR sequences while the patients is lying in the same machine. After the injection of 10-15 mCi of F-18 FDG (0.14 mCi/kg; approximately 5-7 mSv radiation dose), the PET images will be obtained with the patient's arms raised to cover between the orbitomeatal line and the proximal third of the femurs. The study length will not be increased by the addition of PET images, as the image acquisition of PET and MR images is simultaneous.

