#### **1) Objectives**

- a) Test and validate a quantitative multiparametric scoring system combining measurements of MR diffusion, perfusion, stiffness and hypoxia against histopathologic measures of tumor grade, cellularity, aggressiveness, angiogenesis, hypoxia and microvascular invasion in HCC.
- b) Assess the role of combined FDG-PET and MRI for assessment of HCC tumor characteristics in a pilot study in a small subset of patients with HCC.
- c) Compare the diagnostic performance of MRI to ultrasound elastography (ARFI: Acoustic Radiation Force Impulse) to measure liver and HCC stiffness.

	Protocol Name:	Evaluation of HCC Response to Systemic Therapy with Quantitative MRI
	Principal Investigator:	[name]
	Primary Contact Name/Contact Info:	[name] [contact] [contact]
	Date Revised:	6/30/2017
	Study Number:	GCO12-0214

- d) Correlate advanced imaging findings with gene expression profiles measured in resected or biopsy tumor samples.
- e) Assess the predictive value of multiparametric MRI in patients with advanced HCC treated with systemic therapy and/or Yttrium 90 radioembolization.

Hypothesis: There is a negative correlation between diffusion metrics (D: true diffusion coefficient and ADC) and tumor grade/cellularity and aggressiveness; a positive correlation between PF (perfusion fraction) measured with IVIM, arterial fraction (ART) measured with DCE-MRI and each of MVD (microvessel density) and VEGF expression; and a positive correlation between  $\Delta R2^*$  (measured with BOLD) and each of MVD and HIF 1- $\alpha$  (hypoxia inducible factor 1-alpha) expression.

Hypothesis: FDG-PET parameters correlate with HCC tumor grade, and may add information to MRI metrics.

Hypothesis: There is a correlation between quantitative MRI and PET and certain gene expression profiles in tumors.

*Hypothesis: Quantitative MR parameters may enable prediction and assessment of response to systemic therapy and/or Y90 radioembolization.*

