**Research Radiation Exposure**

Test	mSv/test	# per year	Total mSv/year
PET MRI (10 mCi FDG)	7.0	1	7.0
Total Exposure			7.0 mSv

MRI Diffusion-weighted, DCE-MRI, BOLD, MRE and PET images will be evaluated for:

1. Optimal choice of operator-selected sequence parameters
2. Image quality (resolution, signal-to-noise, artifacts, etc,)
3. Suitability for routine use

The total examination time including the setup and routine MRI, ARFI with or without PET will be approximately 60-90 minutes. A physician will be present for all studies.

During the entire MR procedure (both standard and investigational), the investigator or his team will remain in contact with the patient via an intercom system. A squeeze bulb or closed circuit video camera may also be used.

**ARFI (Acoustic Radiation Force Impulse, Siemens):** ARFI is a new ultrasound machine. Patients will undergo an ultrasound examination of liver with special device called ARFI, for which they will be asked to lie on an examining table, and asked to raise their shirt or clothing above the stomach area. A gel will be applied over the skin, and a probe (a small medical instrument) will be placed on the skin in between the ribs. The ARFI device stays outside of the body the entire time. Measuring the liver stiffness takes about 10-20 minutes and will be done for research purposes. The patients will undergo an ARFI during the first visit with and MRI and during their second visit with an MRI or PET/MRI.

If a subject had a liver biopsy, liver surgery or transplantation as part of their routine clinical care, the pathologic specimen will be analyzed with special histological techniques (using special stains with microscopic evaluation), and final results will be compared with MRI, ARFI and PET/MRI results in order to validate our techniques.

	Protocol Name:	Evaluation of HCC Response to Systemic Therapy with Quantitative MRI
	Principal Investigator:	[name]
	Primary Contact Name/Contact Info:	[name] [contact] [contact]
	Date Revised:	6/30/2017
	Study Number:	GCO12-0214

Gene expression profiles: in patients who undergo liver biopsy, resection of transplantation, we will perform gene expression profiling of tumor samples and liver parenchyma.

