### **Risks Associated With PET-MRI:**

The radiation exposure from the PET injection used in this study is considered small and is not likely to adversely affect the subjects. We do not expect any side effects at all either during or after the scan. Subjects who receive a FDG injection as part of the study should not be the primary caregivers for small children or be in close prolonged physical proximity to women of childbearing age who might or are pregnant, for up to 10 hours after imaging.

Subjects will be exposed to some radiation from the PET. Radiation is measured in units called millisieverts(mSv). Below is a table showing the radiation exposure from each test involved in the study:

Test	Exposure
One PET MRI test	7mSv
One MRI	No radiation exposure at all from MRI

	Protocol Name:	Evaluation of HCC Response to Systemic Therapy with Quantitative MRI
	Principal Investigator:	[name]
	Primary Contact Name/Contact Info:	[name] [contact] [contact]
	Date Revised:	6/30/2017
	Study Number:	GCO12-0214

The maximum amount of radiation a subject would receive for research purposes from any combination of tests in this study is 7mSv per year.

Participants who have PET MRI will receive 7 mSv of radiation exposure from the radiotracer (FDG.) This is greater than average annual background and artificial exposure received yearly by people living in the USA (6.2 mSv), and is greater than the US NRC’s recommended annual limit for additional exposure to the General Public of 1 mSv. It is however less than the NRC recommended yearly occupational exposure limit of 50 mSv.

The investigators will always seek to keep exposure As Low As Reasonably Achievable, by choosing procedures with the lowest exposure possible while achieving study goals.

The investigators understand that any radiation exposure resulting from this study is in addition to exposure that the participants may receive from the test and procedures outside of the study. The study team will instruct participants to let them know about any such tests.

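### Does the mismatch between the FDG activity range and the 7 mSv radiation maximum in the 6/30/2017 protocol call for a change to the plan?

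*Combined protocol and SAP*

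**What the plan says.** Three places in the 6/30/2017 protocol give figures for the FDG scan.

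- **Section 5 f), Procedures, FDG-PET/MRI paragraph:** "After the injection of 10-15 mCi of F-18 FDG (0.14 mCi/kg; approximately 5-7 mSv radiation dose". A fixed activity range, a weight-based figure and a dose range stand together, with no word on which governs.
- **Research Radiation Exposure table:** one row, labelled "PET MRI (10 mCi FDG"), at 7.0 mSv per test, one test per year, total 7.0 mSv.
- **Section 6, Risks Associated With PET-MRI:** "Participants who have PET MRI will receive 7 mSv of radiation exposure from the radiotracer (FDG"), and "The maximum amount of radiation a subject would receive for research purposes from any combination of tests in this study is 7mSv per year". The same section compares 7 mSv with 6.2 mSv (average annual exposure in the USA), 1 mSv (general public limit) and 50 mSv (occupational limit).

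On scale, section 5 f) states that "23 patients will be asked to undergo a single PET/MRI and ARFI study", and objective b) places PET "in a pilot study in a small subset of patients with HCC".

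The later document is the modification form (HRP-213) dated 5/11/18. Part B, question 1, item 5 and question 2, item 5 remove PET/MRI. Question 4 reports 84 patients enrolled, none awaiting follow-up, and plans no re-consent.

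**The concern.** The table ties 7.0 mSv to 10 mCi, the bottom of the permitted activity range. The procedures text gives 7 mSv as the top of the dose range for 10-15 mCi. If dose rises with activity, a reader who trusts the table expects every activity above 10 mCi to exceed 7 mSv. A reader who trusts the procedures text expects 10 mCi to give about 5 mSv. The risk section nevertheless presents 7 mSv both as what each PET participant receives and as a ceiling.

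A stated maximum should correspond to the highest activity the protocol allows. If it corresponds to the lowest, the exposure given for some participants would be too low. What is at stake is the accuracy of a safety statement for at most 23 planned single scans, not a statistical analysis.

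**Working it through.** **Inputs.** Activity 10-15 mCi, 0.14 mCi/kg and about 5-7 mSv (section 5 f)); 10 mCi = 7.0 mSv, one scan per year (exposure table); maximum 7 mSv per year and comparators 6.2, 1 and 50 mSv (section 6). The documents give no dose coefficient. The dose figures below assume that dose is proportional to injected activity, with the same factor at every body weight.

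**Step 1: the table's own figure.** 7.0 mSv × 1 scan = 7.0 mSv per year. The sum is right. The implied factor is 7.0 / 10 = 0.70 mSv/mCi. The table has no row above 10 mCi.

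**Step 2: dose at 15 mCi on three readings.**

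| Reading | Factor (mSv/mCi) | Dose at 10 mCi | Dose at 15 mCi | Against 7 mSv |
|---|---|---|---|---|
| Procedures text, upper ends paired | 7/15 = 0.467 | 4.7 | 7.0 | 0% |
| Procedures text, lower ends paired | 5/10 = 0.50 | 5.0 | 7.5 | 7.5/7 = 1.07, +7% |
| Table factor extended upward | 0.70 | 7.0 | 10.5 | 10.5/7 = 1.50, +50% |

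On the table's factor, intermediate activities give 11 × 0.70 = 7.7 mSv (+10%) and 12.5 × 0.70 = 8.75 mSv (+25%). On the two readings of the procedures text, 10 mCi gives 4.7-5 mSv, not the table's 7.0.

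**Step 3: the weight-based figure.** 10 / 0.14 = 71.4 kg and 15 / 0.14 = 107.1 kg, so 0.14 mCi/kg falls within 10-15 mCi only for about 71-107 kg. At 60 kg it gives 60 × 0.14 = 8.4 mCi, below the fixed range. If the 5-7 mSv belongs to the weight-based figure and the table's factor applies, it covers 5 / 0.70 = 7.1 mCi to 7 / 0.70 = 10 mCi. That is 7.14 / 0.14 = 51 kg to 71 kg, and the fixed range is then what does not fit.

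**Step 4: do the comparisons in section 6 change direction?** At 7 mSv the ratio to 6.2 mSv is 1.13; at 10.5 mSv it is 1.69. Both exceed 1 mSv. As a share of 50 mSv they are 14% and 21%. The section's closing comparison, "It is however less than the NRC recommended yearly occupational exposure limit of 50 mSv", holds at either figure.

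**Step 5: does anything downstream use these figures?** Section 5 e) lists three endpoints. Tumor response is necrosis on a later clinical MRI. Time to progression is "defined as the time from initiating therapy to disease progression according to mRECIST criteria as diagnosed on follow-up routine contrast-enhanced MRI". Overall survival is time to death. None uses PET or a radiation figure. The PET objective is to relate PET parameters to tumor grade, and the mSv statement does not enter it.

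**Step 6: can corrected wording still act?** The 5/11/18 form stops PET/MRI, so no further FDG scan is planned. New wording in the superseded text would change no later exposure.

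**The case for a change.** The strongest case for a change is that removing PET/MRI works only forward. It does not correct what was stated to anyone already scanned, and the modification form plans no re-consent. The word approximately cannot stretch to 5 against 7 mSv at 10 mCi, or 7 against 10.5 mSv at 15 mCi. Reconciling three statements and checking at most 23 records would cost little.

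Much of this stands. The three places do not agree, rounding does not explain the gap, and they must be reconciled if anyone relies on them again. Two limits apply.

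- The larger figures are extrapolations. The table is silent above 10 mCi, and extending it assumes one factor for a 71 kg and a 107 kg patient. If dose per mCi falls with body weight, 15 mCi in a heavy patient could stay near 7 mSv. The documents state neither this nor the contrary. The modification form also mentions an appendix D subject to radiation safety review, which is not among the documents; whether it holds a dosimetry basis cannot be told.
- What remains is a conditional check of past records. The number of scans done, the activities given and the patients' weights are not in the documents. Such a check belongs to the sponsor and the radiation safety committee and alters nothing in the design or analysis.

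**Conclusion.** The inconsistency is genuine but minor and historical. The 7 mSv maximum is not consistently supported above 10 mCi. At 15 mCi the possible excess is 0%, 7% or 50%, assuming dose proportional to activity at all weights, and less if dose per mCi falls with weight. It is an inconsistency between sections, not a failed sum.

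No change to the plan follows because none would gain anything. PET/MRI was withdrawn by the 5/11/18 modification, no listed endpoint depends on it, and the comparisons in section 6 keep their direction even at 10.5 mSv. This conclusion rests on the modification being in force. If PET/MRI were resumed, or if scans were done under the 6/30/2017 text, the procedures paragraph, the exposure table and the risk section would have to be reconciled and any recorded activities compared with the result. Which activity or dose figure is right is for the sponsor and the radiation safety committee and is not judged here.
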